9. RESEARCH METHODS

9.1 Study Design

This is a non-interventional, prospective, post authorisation safety study.

Patients with gMG who are expected to start treatment with efgartigimod at enrolment or are within their first cycle of efgartigimod at enrolment will be eligible to enrol into the efgartigimod cohort. Patients with gMG who have not been exposed to efgartigimod and for whom it is not planned to start treatment with efgartigimod at enrolment will be eligible to enrol into the non-efgartigimod cohort. It is anticipated that 340 patients will be enrolled in each cohort.

Patients will be treated and observed according to normal clinical practice. Participation in this study does not limit the physicians` clinical decision making as to the most appropriate treatment for the patient during the course of the study. No visits or investigations outside of normal clinical practice will be required. The enrolled patients will be followed prospectively until end of study participation, loss to follow up, consent withdrawal, or death, whichever comes first. All adverse events (AEs) will be collected throughout the duration of the study.

Enrolment of patients will be over a 5-year period. The follow up of patients will continue for 5 years from the time the last patient has been enrolled. Patients will be followed regardless of whether they continue or discontinue efgartigimod. Assuming a 5-year enrolment period this will allow for a maximum of 10 years of follow-up and a minimum of 5 years. A patient will be considered to be an efgartigimod exposed patient if he/she has received at least one dose of efgartigimod.

In order to minimise heterogeneity between the two cohorts, patients in the efgartigimod cohort will be matched at enrollment with a patient in the non-efgartigimod cohort for the following criteria:

- Age (\pm 5 years)
- Myasthenia Gravis -Activities of Daily Living (MG-ADL) score (0-5, 5-9, and >9) ([Wolfe, 1999](#))
- Region (within EU and within US)

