gMG treatments at or following enrollment (excluding efgartigimod)	
 Drug name, dose, start and stop dates 
 Acetylcholinesterase inhibitors Corticosteroids Other Immunosuppressants (specify) Monoclonal antibodies (specify) Plasmapheresis/plasma exchange acute Plasmapheresis/plasma exchange chronic IVIg therapy acute IVIg therapy chronic Other 	✓	✓

Category	Variables	Baseline	Follow up
Efgartigimod treatment	
 • Date of administration • Reason for interruption during cycle of treatment • Reason for permanent discontinuation whilst on study 	✓	✓
Other comedications at or following enrollment for conditions other than gMG	
 • Drug name, start and stop dates • Indication 	✓	✓
Live/attenuated vaccinations 2 months prior to enrollment to 2 months after last Vyvgart dose	
 • Live/attenuated vaccine 
 ○ Vaccine ○ Date 	✓	✓
Adverse Events (AEs)/Serious Adverse Events (SAEs)	
 • AEs, SAEs 		✓
Events of interest	See Table 2		✓

*All variables will be collected ONLY if available as part of routine clinical practice

A patient will be considered to be an efgartigimod exposed patient if he/she has received at least one dose of efgartigimod.

Additionally, taking into account the variable follow up time and time interval between cycles, the following will be measured for efgartigimod:

- Number of administrations per year
- Total duration of the exposure
- Total number of administrations

The exposure time window of efgartigimod is 56 days +/-3 days after the last dose.

Events of interest in this study will be pre-specified as per [Table 2](#) below.

Table 2: Pre-specified events of interest

Event of interest	Definition	Measurement
Serious infection	Any serious adverse event coded to the Medical Dictionary for Regulatory Activities (MedDRA) System Organ Class (SOC) of Infection and Infestation. See Section 11 for definition of Serious.	Proportion of patients who report serious infections during the course of the study in the efgartigimod treated cohort compared to the non-efgartigimod cohort. Incidence rate of serious infections per patient-years exposed in the efgartigimod treated cohort compared to the non-efgartigimod cohort.

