282	22%	62	17.3%	27.3%
306	25%	76	20.2%	30.2%

*Rounded down to the nearest whole number

A sample size of 270 is recommended to achieve 5% precision (half width). Considering a drop-out rate of 20%, 340 patients in each arm are needed.

To provide further justification about detecting potential increased risk given the calculated sample size above, the power calculation is presented in Table 4 below assuming 20% incidence proportion in the comparator arm and varied increased incidence proportions in the treatment arm with two-sided 0.05 alpha level using normal approximation. With 270 patients who complete the study in each arm, there is 84% power to detect an 11% risk increase.

Table 4: Power calculations to detect potential increased risk

Risk Increase	Expected Proportion for Comparator Arm	Expected Proportion for Treatment Arm	Completion Status	Sample Size in Each Arm	Power
9%	20%	29%	Completers Only	270	69%
10%	20%	30%	Completers Only	270	77%
11%	20%	31%	Completers Only	270	84%
12%	20%	32%	Completers Only	270	89%
9%	20%	29%	Completers + 30 Drop-outs	300	73%
10%	20%	30%	Completers + 30 Drop-outs	300	81%
11%	20%	31%	Completers + 30 Drop-outs	300	88%
12%	20%	32%	Completers + 30 Drop-outs	300	92%
9%	20%	29%	Completers + 60 Drop-outs	330	77%
10%	20%	30%	Completers + 60 Drop-outs	330	85%
11%	20%	31%	Completers + 60 Drop-outs	330	90%
12%	20%	32%	Completers + 60 Drop-outs	330	94%

Owing to the study design with 5-year enrollment and 5-year follow-up, patients will be followed between 5 to 10 years. A discontinued patient enrolled early and discontinued not soon after enrollment will be included in the analysis with possible long follow-up time. For example, the first enrolled patient discontinued at year 6 will have longer follow-up time than the last enrolled patient who has only 5-year

follow-up at maximum. Therefore, early discontinued patient may still contribute high-quality information with acceptable follow-up time to the analysis. Additional power analysis is provided in Table 4 assuming 270 completers +30 and +60 early discontinued patients being included in the analysis, and there is >80% power to detect a 10% risk increase.

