9.7 Data Analysis

The Full Population will be all patients enrolled.

The Safety Population will include all patients enrolled who have taken at least one dose of efgartigimod for the efgartigimod cohort and all patients enrolled into the non-efgartigimod cohort. All analysis will be based on the Safety Population.

Unless otherwise specified, categorical endpoints will be summarised using counts and percent; continuous endpoints will be summarised using mean, standard deviation, median, minimum and maximum values. Statistical analysis will be mainly descriptive in nature using metrics such as

incidence proportion, exposure-adjusted incidence rate, confidence intervals, etc. Details of the analysis plan will be specified in the Statistical Analysis Plan (SAP).

Primary objective

Descriptive statistics will be used to summarise the long-term safety of efgartigimod, including the occurrence of events of serious infections, in gMG patients treated with efgartigimod compared to gMG patients not exposed to efgartigimod. The number and percentage of patients with AEs/SAEs will be presented. The rate per person-year exposure with a 95% CI will be constructed using asymptomatic normal approximation.

Although no formal hypothesis will be tested in the study, statistical models will be used to test the difference of incidence between treatment cohorts (efgartigimod vs. comparator). Two base models which are widely used to model incidence proportion and incidence rate adjusted by potential confounders will be used:

1. To model incidence proportions, a logistic regression model will be used including patients with event vs. patients without event as the response variable and treatment group and country as covariates.
2. To account for varied follow-up time, a Cox regression model will be used with time to the first occurrence of event for each patient as the response variable, treatment group and country as covariates .

Countries with small sample sizes will be combined with other countries based on the geographic locations. Other covariates may be added to the above base models as described below.

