Balance of the baseline measures, including age, MG-ADL score and region matched at enrollment and other demographic and disease characteristics, will be assessed. The imbalanced measures which are considered to be potential confounders based on clinical judgement will be added to the above base models as covariates. If a large number of imbalanced potential confounders are identified after the enrollment is complete, a propensity score method will be applied instead. More details will be given in the SAP.

Subgroup analyses will be performed using descriptive statistics on the subset of patients who remained on efgartigimod throughout the duration of the PASS. In addition, subgroup analyses of treatment cycle per year or administration per year (four administrations in one cycle if not interrupted), subgroup analyses of time since the last administration of efgartigimod prior to the event occurrence in intervals of every 4 weeks will be performed, and subgroup analysis of patients using efgartigimod as add-on or single treatment will be performed if sample size allows. Since one patient may have multiple same events with different time to the last administration, one patient may be assigned to multiple time intervals.

Events of Interest

Statistical analysis of malignancy and other events of interest will follow the same method as those for serious infections

Exploratory objectives

Descriptive statistics will be used to summarise the long-term safety of efgartigimod for specific subgroups. The number and percentage of patients with AEs/SAEs will be presented. The rate per person-year exposure with a 95% CI will be constructed using asymptomatic normal approximation. This will be done for the following subgroups:

- immunocompromised patients and immunocompetent patients.
- patients treated with monoclonal antibodies and patients not treated with monoclonal antibodies.
- patients who have received live/attenuated vaccine and patients who have not received live/attenuated vaccine.
- patients with moderate to severe renal impairment and patients with normal renal function or mild renal impairment.

Missing values

No imputation will be applied to occurrence of serious infection, malignancy or other safety events.

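### The logistic base model for serious infection ignores length of follow-up, and the plan does not say that the Cox model governs if the two disagree

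*Protocol*

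**What the plan says.** Section 9.7 says that models will be used to test the difference in incidence between cohorts and lists two:

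- For incidence proportions, "a logistic regression model will be used including patients with event vs. patients without event as the response variable". Treatment group and country are the covariates. There is no follow-up term, offset or time horizon.
- "To account for varied follow-up time, a Cox regression model will be used with time to the first occurrence of event for each patient", again with treatment group and country.

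Neither is called primary. Covariates may be added, or a propensity score used, but only for imbalanced baseline measures. The same method applies to malignancy and the other events of interest.

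On follow-up, section 9.5 says that "patients will be followed between 5 to 10 years". Section 9.1 has patients "followed prospectively until end of study participation, loss to follow up, consent withdrawal, or death, whichever comes first". Three statements bear on drop-outs:

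- "All analysis will be based on the Safety Population" (section 9.7)
- "A discontinued patient enrolled early and discontinued not soon after enrollment will be included in the analysis with possible long follow-up time" (section 9.5)
- "No imputation will be applied to occurrence of serious infection, malignancy or other safety events" (section 9.7, missing values)

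The first measure for serious infection in Table 2 is "Proportion of patients who report serious infections during the course of the study in the efgartigimod treated cohort compared to the non-efgartigimod cohort". An incidence rate per patient-years is listed second. The precision and power calculations in section 9.5 use the proportion.

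**The concern.** The chance of ever having a serious infection during the study grows with the time observed. A binary model without a follow-up term therefore estimates a mixture of the drug effect and the difference in observation time. Baseline adjustment does not remove this, because follow-up length is not a baseline measure. Nor does the matching, which uses age, MG-ADL and region but not enrolment date or retention.

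The protocol gives reasons why follow-up could differ. Section 9.2 makes sites and countries depend on market access and launch, which can shift accrual in time. Section 9.9 expects the more severe patients to receive efgartigimod, which can change death and drop-out rates.

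The bias can run either way. A longer-followed efgartigimod cohort produces a false signal; a shorter-followed one hides a real risk, which is the worse error in a safety study. If the logistic and Cox results then disagree on the primary question, the protocol does not say which one to report as the finding.

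**Working it through.** **The plan's own figures.** For 20% vs 31% with 270 per arm and two-sided alpha 0.05:

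- Standard error = sqrt[(0.20×0.80 + 0.31×0.69)/270] = 0.0372.
- z = 0.11/0.0372 − 1.96 = 1.00, so power is 84%, as in Table 4. The other Table 4 cells also reproduce, to within about a point.
- Drop-out inflation is 270/0.8 = 338, against 340 stated.

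The sizing arithmetic is sound. The question is what the proportion measures.

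**Inputs.** From section 9.5: 20% incidence proportion (no time horizon attached), follow-up of 5 to 10 years, 340 per cohort. Assumed: the 20% refers to the mid-range of 7.5 years, the hazard is constant, drop-out is non-informative, and the follow-up gaps are as shown below.

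**Formulas.** h = −ln(0.8)/7.5 = 0.02975 per year; risk(t) = 1 − exp(−h·t); odds ratio (OR) = ratio of risk/(1 − risk), efgartigimod to comparator.

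At this hazard a patient followed for 5 years has a 13.8% risk and one followed for 10 years a 25.7% risk. The logistic model treats them alike.

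| Mean follow-up, efgartigimod vs comparator | True HR | Risks | OR |
|---|---|---|---|
| 7.5 vs 7.5 years | 1.0 | 20.0% vs 20.0% | 1.00 |
| 7 vs 8 years | 1.0 | 18.8% vs 21.2% | 0.86 |
| 6.5 vs 8.5 years | 1.0 | 17.6% vs 22.3% | 0.74 |
| 6.5 vs 8.5 years | 1.3 | 22.2% vs 22.3% | 0.99 |

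Reversing the cohorts inverts the null rows, to 1.16 and 1.35.

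**Drop-out alone.** Assume 30% vs 10% leave after an average of 3 years, with risk(3) = 8.5%:

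- Efgartigimod: 0.7×20% + 0.3×8.5% = 16.6%.
- Comparator: 0.9×20% + 0.1×8.5% = 18.9%.
- OR = 0.85.

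**Both models on the same data.** This is a simulation of 340 per cohort, 1,000 runs per row. The hazard is about 0.030 per year, set so that risk averages 20% over follow-up spread evenly across 5 to 10 years. Drop-out is added on top (0.03 per year in both cohorts, except in the two drop-out rows, which use 0.015 and 0.055).

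| Scenario (mean follow-up, efgartigimod vs comparator) | True HR | Logistic OR, p<0.05 | Cox HR, p<0.05 |
|---|---|---|---|
| Equal (6.7 vs 6.7 years) | 1.0 | 1.00, 4.6% | 1.00, 4.3% |
| Efgartigimod enrolled earlier (7.7 vs 5.7) | 1.0 | 1.39, 38% | 1.00, 4.8% |
| Efgartigimod enrolled later (5.7 vs 7.7) | 1.0 | 0.73, 36% | 1.01, 5.9% |
| Less drop-out on efgartigimod (7.1 vs 6.1) | 1.0 | 1.18, 13% | 1.00, 4.0% |
| More drop-out on efgartigimod (6.1 vs 7.1) | 1.0 | 0.84, 16% | 0.99, 5.1% |
| Equal (6.7 vs 6.7) | 1.6 | 1.70, 81% | 1.61, 82% |
| Efgartigimod enrolled later (5.7 vs 7.7) | 1.6 | 1.22, 18% | 1.62, 77% |

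**The case against.** The strongest reply is that the protocol already holds the right analysis. The Cox model is introduced expressly because follow-up varies, Table 2 pairs the proportion with a rate, and section 9.7 plans person-year rates with confidence intervals. A reader might infer from the logistic model that the plan ignores follow-up altogether. It does not: the stated purpose of the Cox model is itself a reason to prefer it. What is missing is the statement that it leads.

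A second reply is that the study is described as descriptive and that details go to the SAP. The choice of estimator does belong there. But the protocol itself fixes the logistic response and base covariates, and says that the models will test the difference.

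A reader might also infer that every drop-out is counted as event-free. That goes too far: anyone with an event recorded before leaving counts as an event. For the rest, the classification is inferred from the population, inclusion and no-imputation statements together. Section 9.9 leaves complete-records analysis, multiple imputation and a sensitivity analysis open for the SAP, which sits uneasily with section 9.7 but shows that the subject is not ignored.

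Finally, the design limits the gap. Both cohorts share one enrolment window and one closing date, comparators are matched at enrolment, follow-up continues after efgartigimod is stopped, and the retention rules cover everyone. A two-year gap is 40% of the five-year range between minimum and maximum follow-up. The one-year effect is also small against sampling error: with 340 per cohort the 95% interval around 0.86 would run from about 0.59 to 1.26. A true HR of 1.3 (20% vs 25.2% with equal follow-up) would have only about 30% to 36% power at 270 to 340 per arm. All of this stands, and it limits the weight of the point without removing it.

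**Conclusion.** The point holds in a limited form. The logistic base model has no means of handling unequal follow-up, and the plan leaves it unranked beside the Cox model while Table 2's first measure and the study size rest on the crude proportion.

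The bias is conditional. It is zero with equal follow-up and drop-out. Under the stated assumptions it gives an odds ratio of about 0.86 for a one-year shortfall on efgartigimod and 0.74 for two years, with the reverse if efgartigimod is followed longer. The protocol does not show that such a gap will occur; it only does not prevent one. Constant hazards and non-informative drop-out are assumed throughout, and the Cox model relies on the second of these as well.

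A reader might take this to mean that the sample size is wrong or that the study cannot answer its question. Neither follows: the sizing figures reproduce, and a comparison that accounts for follow-up is already planned. This should be corrected, but it does not undermine the study.

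**What to change.** In section 9.7:

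1. Name the Cox model as the lead cohort comparison, and say that it governs if the models disagree.
2. Replace the crude logistic odds ratio with a comparison of cumulative incidence that handles censoring (Kaplan-Meier, or Aalen-Johansen with death as a competing event), or keep it marked as supportive to that comparison. Report risk at 5 years, which every completer reaches by design, and at later time points too, so that late events such as malignancy are not lost.
3. Report follow-up time, and the reasons for its ending, by cohort.

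Align the proportion measures in Table 2 with item 2. The technique for the adjusted risk comparison can be left to the SAP.

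The cost is wording in section 9.7 and Table 2 and slightly more analysis, with no new data. Risk estimates beyond year 5 will be less precise, because fewer patients are followed that long.

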With the exception of AChE inhibitors, the complement inhibitor eculizumab, and a liquid formulation of azathioprine, which have received regulatory approval in Europe for the treatment of gMG, all other existing therapies are used off-label [Vyvgart EPAR].

In the United States (US), efgartigimod is approved for the indication of gMG in adult patients who are AChR antibody positive and in the EU it is approved as an add-on to standard therapy for the treatment of adult patients who are AChR antibody positive.

The recommended dose of efgartigimod is 10 mg/kg as a 1-hour intravenous infusion to be administered in cycles of once weekly infusions for 4 weeks. Subsequent treatment cycles are administered according to clinical evaluation. The frequency of treatment cycles may vary by patient.

In the EU Risk Management Plan (RMP) for efgartigimod, serious infections, is considered to be an important potential risk. As efgartigimod induces a transient lowering in IgG levels, there is a potential

risk for infections associated with the lowered IgG levels. In the randomized placebo-controlled study of 167 patients ARGX-113-1704, 84 patients with gMG were exposed to efgartigimod and the most frequently observed adverse reactions were upper respiratory infections (10.7% in the efgartigimod patients and 4.8% in the placebo patients) and urinary tract infections (9.5% in the efgartigimod patients and 4.8% in the placebo patients). In the patients who received efgartigimod, these events were \leq Grade 2 according to the Common Terminology Criteria for Adverse Events (CTCAE). Overall, treatment emergent infections were reported in 46.4% of patients treated with efgartigimod and 37.3% of patients treated with placebo. The frequency of infections in the efgartigimod treated patients did not increase with repeated cycles of treatment. There were no serious infections or opportunistic infections in the efgartigimod treated patients. This study will evaluate the occurrence of serious infections in gMG patients treated with efgartigimod in the real world setting under conditions of normal clinical practice compared to gMG patients who are not treated with efgartigimod.

During clinical development of the IV formulation, in the efgartigimod phase 3 placebo-controlled 26 week clinical study, ADAPT, there were 2 reported neoplasm events, 1 (1.2%) in the efgartigimod treatment arm and 1 (1.2%) in the placebo treatment arm.

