Malignancy	Any adverse event (AE) within the Standardised MedDRA Query (SMQ) Malignancies (Narrow) .	Proportion of patients who report events of malignancy during the course of the study in the efgartigimod treated cohort compared to the non-efgartigimod cohort. Incidence rate of events of malignancy per patient-years exposed in the efgartigimod treated cohort compared to the non-efgartigimod cohort.
Adverse event (AE)	Any untoward medical occurrence in a patient administered a pharmaceutical product or device and that does not necessarily have a causal relationship between the product and the event. An AE can, therefore, be any unfavorable or unintended sign (including an abnormal laboratory finding) or symptom temporally associated with a medicinal product, whether or not related to the medicinal product.	Proportion of patients who report AEs during the course of the study in the efgartigimod treated cohort compared to the non-efgartigimod cohort. Incidence rate of AEs per patient-years exposed in the efgartigimod treated cohort compared to the non-efgartigimod cohort.
Serious adverse event (SAE)	As per definition in Section 11.	Proportion of patients who report SAEs during the course of the study in the efgartigimod treated cohort compared to the non-efgartigimod cohort. Incidence rate of SAEs per patient-years exposed in the efgartigimod treated cohort compared to the non-efgartigimod cohort.

AEs (serious and non-serious) in immunocompromised patients
	
Immunocompromised definition (moderate or severe) based upon Centre for Disease Prevention (CDC) People Who Are Immunocompromised CDC.
	
Proportion of AEs/SAEs reported in immunocompromised patients and immunocompetent patients in the efgartigimod cohort.
 
Incidence rate of AEs/SAEs per patient-years exposed in immunocompromised patients and immunocompetent patients in the efgartigimod cohort.

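### For frequent events, chiefly any AE, the adjusted comparisons in Section 9.7 use at most one event per patient and carry little information on later years or repeat events

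*Protocol*

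**What the plan says.** Table 2 (Protocol, Section 9.3) gives each safety event two measures. One is the proportion of patients with the event. The other is a rate: for AEs, "Incidence rate of AEs per patient-years exposed in the efgartigimod treated cohort compared to the non-efgartigimod cohort"; for serious infection, "Incidence rate of serious infections per patient-years exposed in the efgartigimod treated cohort compared to the non-efgartigimod cohort". SAEs and malignancy have the same form. The table does not say whether a patient's second and later events enter the numerator.

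Section 9.7 then names the adjusted analyses: "Two base models which are widely used to model incidence proportion and incidence rate adjusted by potential confounders will be used". The first is logistic regression on patients with and without the event. The second is meant to account for varied follow-up: "a Cox regression model will be used with time to the first occurrence of event for each patient as the response variable". The method is carried over to the rest of Table 2: "Statistical analysis of malignancy and other events of interest will follow the same method as those for serious infections". Table 2 lists any AE and any SAE as events of interest, so both are included.

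Separately, Section 9.7 reports a descriptive rate: "The rate per person-year exposure with a 95% CI will be constructed using asymptomatic normal approximation". No adjustment is attached to it.

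**The concern.** Both adjusted models use at most one event per patient. That suits an uncommon event. It suits any AE poorly over 5 to 10 years of follow-up: nearly every patient will have had one, so the logistic outcome is close to constant, and the Cox model stops using a patient after the first AE, usually early.

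Section 7 lists long-term safety as missing information and gives a maximum of 721 days of treatment and follow-up so far (721/365.25 = 1.97 years). For any AE, the adjusted comparison would therefore draw mainly on the period for which some data already exist, and little on the years the study was set up to observe. An increase that builds late, or that appears as repeat events, would largely escape both adjusted analyses.

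**Working it through.** **The plan's own figure first.** Table 4 gives 84% power for 20% v 31% with 270 per arm. Pooled proportion 0.255; null SE = √(2 × 0.255 × 0.745/270) = 0.0375; alternative SE = √((0.16 + 0.2139)/270) = 0.0372; (0.11 − 1.96 × 0.0375)/0.0372 = 0.98; power = Φ(0.98) = 83.7%. It reproduces, as do the other Table 4 rows within rounding. The sample size is not in question.

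**Inputs for any AE.** Section 7: "treatment emergent infections were reported in 46.4% of patients treated with efgartigimod and 37.3% of patients treated with placebo". The period is taken as 26 weeks (0.5 year), assuming this placebo-controlled study is the 26-week study described in the same section. Infections are a subset of AEs, so they give a lower bound for any AE.

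**Time to first event, placebo figure.**
- Constant hazard: −ln(1 − 0.373)/0.5 = 0.934 per year. With an event by year 1: 1 − e^(−0.934) = 61%; year 2: 85%; year 5: 99%.
- Gamma frailty, variance 1: rate = (1/0.627 − 1)/0.5 = 1.19 per year. By year t: 1 − 1/(1 + 1.19t), giving 54%, 70% and 86% at years 1, 2 and 5.
- The 46.4% figure gives 92% by year 2 (78% with frailty).
- If routine care captured events at only half the trial hazard (0.467 per year): 61% by year 2 and 90% by year 5.

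**Follow-up used.** Share of a 7.5-year follow-up that precedes the first event: (1 − e^(−0.934 × 7.5))/(0.934 × 7.5) = 14%; with frailty, ln(1 + 1.19 × 7.5)/(1.19 × 7.5) = 26%.

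**Power for any AE.** Simulation with 340 per cohort, follow-up uniform on 5-10 years, 20% drop-out, two-sided 0.05, placebo-based rates as above. First-event Cox is compared with an all-events rate ratio using patient-level robust variance. Ranges cover no frailty, frailty variance 1, and repeated runs.

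| AE rate on efgartigimod | Cox HR | Cox power | All-events ratio | All-events power |
|---|---|---|---|---|
| 30% higher from year 2 | 1.03-1.05 | 7-12% | 1.21-1.22 | 60-100% |
| 50% higher from year 2 | about 1.06 | 9-12% | 1.35-1.36 | 94-100% |
| 30% higher from enrolment | 1.16-1.30 | about 90% without frailty, 33-43% with | 1.30 | 87-100% |

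**Serious infection.** Section 9.5 assumes 20%. Over 7.5 years the hazard is −ln(0.8)/7.5 = 0.0298 per year. Of first events in that time, (1 − e^(−0.0298 × 2))/0.2 = 29% fall by year 2, so the comparison is not decided early. Keeping 20% with an event, mean counts are 0.25 (frailty variance 1) and 0.281 (variance 2), so recurrences are 1 − 0.2/0.25 = 20% and 1 − 0.2/0.281 = 29% of events. For a rate ratio of 1.66 from enrolment, Cox power is 67-80% against 77-89% for all events. For a ratio of 1.5 from year 2 without frailty it is about 42% against 50%.

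**Interval for the descriptive rate.** If repeat events count, events within a patient are correlated. With frailty variance 1 and mean count 1.19 × 7.5 = 8.9, the variance is 1 + 8.9 = 9.9 times the Poisson value. An interval treating events as independent would have about 1/√9.9 = 32% of the correct width. Section 9.7 does not say which variance is meant.

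**The case against.** **The rate is reported.** The analysis is described as mainly descriptive, and Section 9.7 gives a rate per person-year with a 95% CI. A reader might infer that the plan cannot show a long-term AE difference at all. That is not supported: if counts include repeat events, the descriptive rates can show one. They are unadjusted, however, and Section 9.9 expects the more severe patients to receive efgartigimod. Matching on age, MG-ADL band and region removes part of that imbalance, but the adjusted models exist because the protocol does not rely on matching alone.

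**The numerator is not stated.** A reader might infer a direct contradiction between Table 2 and Section 9.7. The text does not go that far: a rate of AEs per patient-year reads as a count of events, but it could mean first events. The one remark on repeats, "Since one patient may have multiple same events with different time to the last administration, one patient may be assigned to multiple time intervals", concerns the subgroup tabulation by time since last administration and sets no rule for the cohort rates. This stands; it makes the text ambiguous, not contradictory.

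**The late-onset scenario is chosen.** Section 7 links the risk to a transient fall in IgG and reports no rise in infections with repeated cycles. An effect present from enrolment is visible to Cox, at about 90% power without frailty. That also stands, but power falls to 33-43% with frailty, and the later years are where Section 7 says information is missing.

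**Other analyses help.** Subgroups by cycles or administrations per year, patients remaining on efgartigimod, and tables by SOC and PT give partial cover. They are descriptive.

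**This could wait for the SAP.** The exact recurrent-event model could. But Section 9.7 already fixes the response variable as the first event and extends it to all events of interest.

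**Conclusion.** The point holds for frequent events, chiefly any AE and to a lesser and unquantified degree SAEs. The protocol names no adjusted comparison that uses all events, and its adjusted any-AE comparisons are largely exhausted by about year 2 (85% of patients at a constant hazard, 70% with frailty variance 1). A late 30% rise would be detected 7-12% of the time by Cox, against 60-100% by an all-events analysis.

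It should not be read as a failure of the serious-infection comparison. That event drives the study size, the loss there is moderate, and first-event Cox is acceptable for it and for malignancy.

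The size rests on four assumptions: 26 weeks as the period for the infection percentages, trial rates carrying over to routine care, infections as a lower bound for any AE, and the stated frailty range. Halving the hazard still leaves 61% with a first event by year 2. This is worth correcting before the analysis is fixed; it does not undermine the design or the sample size.

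**What to change.** - **Table 2:** state that the rate numerator counts all events or, if that is the intention, first events only.
- **Section 9.7:** add an adjusted recurrent-event model, either negative binomial with a log person-time offset or Andersen-Gill with robust variance, with the same covariates as the Cox model. Apply it to AEs and SAEs, and to serious infection as a supplementary analysis.
- **Confidence intervals:** use patient-clustered variance for event rates.
- **Keep** first-event Cox for serious infection and malignancy. Label the any-AE logistic and first-event results descriptive.

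The cost is one added model and some wording. AEs are already collected throughout follow-up, so no new data collection and no change in sample size are needed. The small downside is that a rule is needed for when a repeat report counts as a new event.
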